### 3.5.7.2 Safety Analysis

If no SAEs are observed in 1348 STM patients who received V212, this study provides 97.5% confidence that the true SAE rate is <0.28% (1 out of every 362 patients).

The probability of observing at least one SAE in this study depends on the number of patients enrolled and the incidence rate of SAEs in the general population. If the incidence rate of a SAE is 1 of every 838 recipients of the vaccine (0.12%), then there is an 80% chance of observing at least one such SAE among 1348 patients in the vaccine group. If the incidence rate is 1 of every 1943 recipients (0.05%), there is a 50% chance of observing at least one SAE.

For safety comparisons, risk differences between the 2 vaccination groups that could be detected with a 80% probability are summarized in Table 3-4 for a variety of hypothetical true incidence rates. These calculations assume there are 1348 and 1348 STM patients for safety in the vaccine and placebo groups and are based on a 2-sided significance level of  $\alpha = 0.05$ . No multiplicity adjustments were made in these calculations.

**Table 3-4**  
**Differences in Incidence of Adverse Experience Rates Between the Two**  
**Vaccination Groups That Can Be Detected With an ~80% Probability and a Two-Sided**  
**Significance Level of 0.05, With Total 2696 STM Patients**

True Incidence Rate of Adverse Experience in Vaccine Group (%)	True Incidence Rate of Adverse Experience in Placebo Group (%)	Detectable Percentage Points Difference in Incidence Rates of Adverse Experiences
0.5	1.59	1.09
1	2.39	1.39
3	5.12	2.12
5	7.61	2.61
8	11.16	3.16
10	13.45	3.45
20	24.46	4.46
30	35.03	5.03

Note: These incidence rates are hypothetical and do not represent actual incidence rates of specific adverse experiences in either group.

### **3.5.7.3 Immunogenicity Analysis**

All immunogenicity analyses in this study are exploratory. A subset of patients (n ~ 1000) will participate in the ELISPOT substudy and undergo testing for direct VZV T-cell responses by IFN- $\gamma$  ELISPOT assay. This substudy size is required to adequately power ( $\approx 70\%$ ) the study to detect correlation with efficacy for combined STM and HM population when assuming the true correlation is one unit increase of log scaled post dose 4 ELISPOT GMC will reduce the HZ risk by 18% and standard deviation of log scaled post dose 4 ELISPOT GMC is 2.2 for HM and 1.6 for STM. This substudy size also provides sufficient power ( $>88\%$ ) for each subgroup population for testing fold difference at lower bound of 1.0 when the true fold difference between two groups is 2.0.

In addition, T-cell responses will be indirectly measured using an antibody measure, gpELISA in all patients from STM subgroup. The GMT or GMC and GMFR for gpELISA and ELISPOT will be provided by vaccination group at scheduled time points (see Section 1.7). A longitudinal regression model will be used to estimate the fold difference at these time points between the vaccination groups, while adjusting for the prevaccination titers. Other exploratory analyses will also be performed to determine whether these VZV-specific immune responses are associated with protection against HZ using Cox proportional hazards models.

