## 1.4 SUMMARY OF STUDY DESIGN

Approximately 5264 patients (~2568 HM patients; ~2696 STM patients), 18 years of age or older will be equally randomized to receive a 4-dose regimen of either V212 or placebo. (**Note: In India only, enrollment is restricted to patients 18 to 65 years of age.**) Patient allocation will be double-blinded, with in-house blinding procedures. Enrollment for this study is expected to be completed in approximately 36 months. Study duration is anticipated to be approximately 5 years from the date the first patient is enrolled.

This is an event-driven study based upon the occurrence of confirmed HZ cases. HZ rates will be monitored on an ongoing basis using the blinded database. The primary efficacy analysis will be conducted after at least 90 confirmed HZ cases have been accrued in the STM population. Patients will remain in the study from the time of enrollment until accrual of the targeted number (~90) of confirmed HZ cases. This study uses an adaptive design based on pre-specified criteria, using an independent, external Data Monitoring Committee (DMC) to monitor safety and efficacy. The study will be conducted based on 2 key efficacy milestones as listed below:

- When at least 50% of the required confirmed HZ cases have accrued for each population, HM and STM, interim futility analysis will be conducted for each group (completed 29-Oct-2014).
- When 90 confirmed HZ cases have accrued in the STM population, the database will be unblinded and the final efficacy analysis will be conducted. Of note, if the observed HZ case accrual rate indicates that more than 5 years of patient follow-up will be necessary to accrue the targeted number of confirmed cases, then the SPONSOR will consider it beyond the adjustment cap and terminate the study after approximately 5 years of patient follow-up have occurred (from the date the first patient is enrolled).

During the interim analysis, a futility analysis was conducted to assess whether efficacy met a pre-specified level. The analysis was conducted separately for each patient population (HM and STM) when at least 50% of required HZ cases had accrued in the corresponding population (29-Oct-2014). Analysis results were evaluated by the DMC with the following outcome:

HM population: solid statistical evidence of futility for the primary endpoint. Thus, enrollment and vaccination was stopped on 04-Nov-2014 and study close-out procedures in this population began on 19-Nov-2014.

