#### **2.1.4 Exploratory Objectives**

1. To assess the safety and tolerability of V212 when administered to adults with HM.
2. To assess the impact of V212 on the development of HZ in adults with HM.
3. To assess the impact of V212 on the development of moderate to severe HZ-associated pain at any time from HZ onset through the end of the 6 month HZ follow-up period. Moderate to severe HZ-associated pain is defined as 2 or more occurrences of a score of 3 or greater (0-to-10 scale) on the Zoster Brief Pain Inventory (ZBPI) in adults with HM.

4. To assess the impact of V212 on the development of HZ complications defined as the occurrence of any of the following during the study: hospitalization or prolongation of hospitalization due to HZ, disseminated HZ (including disseminated HZ rash or VZV viremia), visceral HZ, ophthalmic HZ, neurological impairment due to HZ, or administration of intravenous acyclovir therapy for treatment of HZ in adults with HM.
5. To assess the impact of V212 on the development of PHN. PHN is defined as a worst pain score (in the previous 24 hours) of 3 or greater (0-to-10 scale) on the ZBPI, that persists or appears greater than or equal to 90 days after the onset of HZ rash in adults with HM.
6. To assess the immunogenicity of V212 in adults with STM or HM.
7. To describe the impact of HZ on activities of daily living (ADL) and quality of life (QoL), and to assess the impact of V212 on interference with ADL and QoL in study patients who develop HZ.
8. To describe HZ-related non-protocol-mandated health care resource utilization (HCRU), and assess the impact of V212 on HZ-related non-protocol-mandated HCRU, and work and productivity loss (WPQ).
9. To assess the impact of V212 on the severity and duration of HZ-related pain.
10. To assess the impact of V212 on the severity of HZ rash including the extent of rash, number of skin lesions present, and number of dermatomes involved.
11. To assess the association of immunogenicity at postvaccination with the risk of HZ in adults with STM or HM.

The exploratory objectives (1)-(5) will be evaluated for HM only; objectives(6)-(10) will be evaluated for STM and HM separately and (11) will be evaluated in both combined STM and HM populations and individual subpopulation.

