### **2.5.3 Immunogenicity Measurements**

The study will provide an exploratory immunogenicity assessment of V212, as shown in Table 2-2. The goal is to assess the immunogenicity of the vaccine and to attempt to demonstrate correlation of immune responses to the vaccine with clinical efficacy. Serum VZV antibody levels will be measured by gpELISA in patients in the STM study group. Serum samples will be collected on Day 1/Visit 1 (prior to Dose 1) and Visit 5 (~28 days Postdose 4) based on the original enrollment plan (~2696 patients).

A subset of the study population will be enrolled in an ELISPOT substudy to measure T cell response by IFN- $\gamma$  ELISPOT. Peripheral blood mononuclear cells (PBMC) will be collected from those enrolled in the ELISPOT substudy (n ~ 1000), on Day 1/Visit 1 (prior to Dose 1) and Visit 5 (~28 days Postdose 4). Participation in the ELISPOT substudy will be limited to select sites based upon accessibility to PBMC processing laboratories. At these sites, the first 500 patients enrolled in the STM group and the first 500 enrolled in the HM group will be enrolled in the ELISPOT substudy.

Patients enrolled in the ELISPOT substudy will have a separate allocation schedule to assure a well-balanced randomization ratio. All investigative sites participating in the ELISPOT substudy will enroll each consented patient into the ELISPOT substudy until the target enrollment of 1000 patients has been met.

Table 2-2

Exploratory Immunogenicity Assessment of V212

Assay	Goal	Population
gpELISA	Assess T cell-dependent antibody response	

• STM = ~2696 patients

• HM = none

IFN- $\gamma$ ELISPOT	Assess T cell response	

• STM = ~500 patients*

• HM = ~500 patients*

\* Limited to select sites with adequate laboratory processing capabilities

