### **3.2.12 Stratification/Randomization/Allocation**

Randomization will be stratified by patient population (STM or HM) with approximately 2696 patients with STM and 2568 patients with HM enrolled into the study. Patients with HM will be further stratified into one of two strata (low IC; moderate to high IC), based on the patient's specific HM diagnosis (underlying cancer diagnosis) and/or chemotherapeutic regimen (see Appendix 6.1). The planned randomization schedule by vaccination group is shown in Section 2.4.2.

An IVRS will be used to register patient visits at the time of randomization and at subsequent visits. The IVRS will be used to allocate the patient to the vaccination group assignment and to assign either V212 or placebo to the patient during randomization, according to a centralized randomization schedule generated by the SPONSOR. Study site personnel accessing the IVRS will be assigned an individual unique personal identification number (PIN). Site personnel must use only their specific assigned PIN to access the IVRS and must not share their assigned PIN with anyone.

A separate allocation schedule will be used to allocate those patients participating in the ELISPOT substudy to assure a well-balanced randomization ratio. All investigative sites participating in the immunogenicity substudy will enroll each consented substudy patient until the target enrollment of 1000 patients has been met.

At Visit 1, after the patient has signed the consent form, the medical history has been collected, all inclusion/exclusion criteria are met, a negative serum or urine pregnancy test (sensitive to 25IU  $\beta$ -hCG) has been obtained, and the prevaccination blood sample has been collected (if applicable), site personnel will access the IVRS using their PIN. The IVRS will assign an allocation number to the patient, followed by the assignment of unique component identification number (CID) corresponding to the vial of vaccine/placebo and diluent the patient should receive at that visit. The CID on the vaccine/placebo vial and the CID on the diluent vial will be unique. The IVRS will automatically assign the appropriate clinical material based on the patient's treatment allocation.

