### **3.5.1 Responsibility for Analyses**

The statistical analysis of the data obtained from this study will be the responsibility of the designee/Clinical Biostatistics department of the SPONSOR.

This study will be conducted as a double-blind study under in-house blinding procedures. The official, final database will not be unblinded until medical/scientific review has been performed, protocol violators have been identified, and data have been declared final and complete.

This study is event-driven, with one interim futility analysis and one final efficacy analysis. The interim analysis included futility analyses for individual subgroups (HM and STM). The interim futility analysis was done when at least 50% of the total number of required evaluable HZ cases in each patient population, HM and STM, had accrued. More specifically, the futility analysis was conducted on the HM population when at least 68 cases had accrued in the HM subgroup and the futility analysis was conducted on the STM population when at least 48 cases had accrued in the STM subgroup.

The DMC will monitor safety periodically and will be responsible for reviewing the results of the planned formal interim analyses. The DMC may recommend stopping the study early based on safety concerns or futile efficacy results from the interim futility analysis (see Section 3.5.8.1 and DMC guidelines).

An unblinded SPONSOR statistician who is otherwise unrelated to this protocol will serve as a non-voting member of DMC and will be responsible for performing these preliminary/interim analyses for DMC. Detailed implementation of the interim analysis is described in the DMC charters (separate documentation).

All the interim analysis data will remain blinded to SPONSOR study personnel, the study investigator, the laboratory staff, the CAC members, and the patients throughout the study, until the final database unblinding when all required evaluable HZ cases are accrued.

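### The ≈70% power in 3.5.7.3 for the combined ELISPOT correlate fits the original 232-case design and was not updated when HM closed and STM was set at 90 cases; about 50–65% is now more likely

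*Combined protocol and SAP*

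**What the plan says.** Section 3.5.7.3 justifies the substudy of about 1000 patients by its power to detect a relation between ELISPOT response and HZ: "This substudy size is required to adequately power ( $\approx 70\%$ ) the study to detect correlation with efficacy for combined STM and HM population". The assumed effect is that "one unit increase of log scaled post dose 4 ELISPOT GMC will reduce the HZ risk by 18" per cent, and the assumed spread is that "standard deviation of log scaled post dose 4 ELISPOT GMC is 2.2 for HM and 1.6 for STM". The section gives neither the number of HZ cases nor the significance level behind the ≈70%.

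Section 2.5.3 says who enters the substudy at participating sites: "the first 500 patients enrolled in the STM group and the first 500 enrolled in the HM group". The trial as a whole planned "approximately 2696 patients with STM and 2568 patients with HM enrolled into the study" (3.2.12).

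The analysis is still planned in this version. Section 2.1.4 says that objective "11) will be evaluated in both combined STM and HM populations and individual subpopulation".

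The case numbers have changed. Section 3.5.1 says that "the futility analysis was conducted on the HM population when at least 68 cases had accrued in the HM subgroup", which was the 50% mark. Section 1.4 says that in HM "enrollment and vaccination was stopped on 04-Nov-2014 and study close-out procedures in this population began on 19-Nov-2014". Sections 1.4 and 3.1.2 set the STM target at 90 cases. The summary of changes lists 3.5.7.1 (primary power) and 3.5.5.2 as revised, but not 3.5.7.3.

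**The concern.** The precision of a Cox slope comes from cases, not from patients sampled. HM was expected to supply most of it, because it had more cases and a larger spread of the marker. If the ≈70% was worked out for the full HM and STM case targets, closing HM part-way removes much of the information while the number of blood samples stays the same. The current text, in the present tense, would then describe a trial that is no longer being run.

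What is at stake is how objective 11 is read. A flat slope from an analysis described as adequately powered carries more weight than one from an analysis with roughly an even chance of detecting the assumed effect.

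**Working it through.** **Inputs from the documents.** Hazard ratio 0.82 per log unit; SD 2.2 (HM) and 1.6 (STM); 500 substudy patients per population; 2568 HM and 2696 STM planned.

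Original case targets: 68 and 48 were the 50% marks (3.5.1), so 2 × 68 = 136 HM and 2 × 48 = 96 STM, total 232. Two other figures in Appendix 6.3 agree: the second look at 174 combined cases was 75% of the total (174 / 0.75 = 232), and Table 3-8 gives 83 + 149 = 232 for the final combined analysis. The 210 STM cases mentioned in 3.1.2 belong to the enlarged STM-only scenario, not to this total.

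**Assumptions.** Two-sided 0.05; substudy cases in proportion to the substudy's share of each population. Results are shown with all cases evaluable and with 90% evaluable, since some cases will lack a usable postdose-4 sample. The 90% is an assumption.

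**Formula.** With θ = ln 0.82 = −0.1985 and θ² = 0.03938,

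information I = θ² × [HM cases × (500 / HM enrolled) × 2.2² + STM cases × (500 / 2696) × 1.6²]

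power = Φ(√I − 1.96)

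**Reproducing the stated figure.** Substudy cases: 136 × 500/2568 = 26.5 HM and 96 × 500/2696 = 17.8 STM, about 44 in all.

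- Population-specific SDs: I = 0.03938 × (26.48 × 4.84 + 17.80 × 2.56) = 6.84; √I = 2.616; power 74.4%. With 90% evaluable: 69.9%.
- One averaged SD of 1.9: I = 0.03938 × 44.28 × 3.61 = 6.30; power 70.9%.
- A simulated Cox model stratified by population, with 26 + 18 cases, gave 74%.
- Other significance levels fit less well: one-sided 0.05 gives 80–83%, two-sided 0.025 gives 60–65%.

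So ≈70% is consistent with 232 cases at two-sided 0.05. HM supplied 74% of that information (26.48 × 4.84 = 128.2, out of 128.2 + 45.6).

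**Current design, 68 HM + 90 STM cases.** Substudy cases: 13.2 + 16.7, about 30. I = 0.03938 × (13.24 × 4.84 + 16.69 × 2.56) = 4.21, which is 61% of the original. Power is 53.6%, or 49.4% with 90% evaluable. Simulation with 13 + 17 cases gave 53%.

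**Varying what the documents do not give** (STM at 90 cases throughout):

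| HM cases | HM enrolled | Power, all evaluable | Power, 90% evaluable |
|---|---|---|---|
| 68 | 2568 | 53.6% | 49.4% |
| 80 | 2568 | 57.8% | 53.4% |
| 90 | 2568 | 61.1% | 56.6% |
| 100 | 2568 | 64.2% | 59.6% |
| 120 | 2568 | 69.7% | 65.2% |
| 68 | 2000 | 60.2% | 55.8% |
| 80 | 2000 | 65.0% | 60.4% |
| 90 | 2000 | 68.6% | 64.0% |
| 100 | 2000 | 71.9% | 67.3% |

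The fall in the STM target hardly matters: 136 HM + 90 STM would still give 73.7%. Almost all of the loss comes from closing HM.

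**STM alone, 90 cases.** 16.7 substudy cases; I = 0.03938 × 16.69 × 2.56 = 1.68; power 25.4%, or 23.3% with 90% evaluable.

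**The case against.** The strongest reply is that the loss cannot be pinned down. Sixty-eight HM cases is a minimum. The flow-chart notes in 1.7 and the completion procedures in 3.2.19 keep patients under efficacy follow-up for at least a year after the last dose, and 3.2.19 expressly includes new HZ cases. The superseded plan in Appendix 6.3 said that a closed arm would accrue no further cases, so the final HM count is open. HM enrolment at closure is not given either; a smaller total raises the substudy's share of HM cases. The first 500 patients at the participating sites may also have had longer follow-up than the rest. If, purely as an illustration, that added 20% to the information at 80 HM cases, power would be 61–66% with 2568 enrolled (I = 4.65 × 1.2 = 5.58 with all evaluable) and 68–73% with 2000 (5.50 × 1.2 = 6.59). Cases before Visit 5, missing samples and adjustment for baseline response pull the other way. All of this stands. A reader might infer that power is now a firm 50–60%, or that the objective is certainly underpowered; the documents do not support either.

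It is also fair that the plan calls every immunogenicity analysis exploratory, speaks only of attempting to show a correlation, and already plans a Cox risk ratio for the marker. A reader might infer that the plan would treat a non-significant slope as absence of correlation, but nothing in it says so. Nor does it claim any correlate power for STM alone, so the 23–25% above contradicts no statement, and gpELISA in all STM patients also serves the objective there.

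What does not stand is that the sentence merely records the original sizing. Superseded interim text was moved to Appendix 6.3 and labelled as such. This sentence sits unlabelled in the current section, and 3.5 says that no separate SAP will be issued.

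**Conclusion.** The ≈70% is consistent with the original 232-case design and was carried forward unchanged. That it rests on 232 cases and two-sided 0.05 is an inference from a good match, since 3.5.7.3 states neither.

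At the minimum HM count, power is about 49–54%. At 80–100 HM cases and planned enrolment it is about 53–64%. Most inputs give about 50–65%; a return to about 70% needs favourable conditions together, or close to the full original HM case count. These figures assume proportional substudy shares and the plan's own effect size and SDs.

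This is a minor correction. It touches an exploratory objective and does not affect the primary analysis, its alpha or any stopping decision.

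**What to change.** In 3.5.7.3:

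1. State the number of HZ cases in the substudy and the significance level on which the power rests.
2. Replace ≈70% with the figure recalculated from the blinded HM and STM case counts in the substudy. Until those counts are available, give the range with its assumptions: about 50–65% under most inputs.
3. If a figure for STM alone is wanted, give about 23–25% at 90 cases.

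The cost is protocol wording and a short calculation on blinded counts. No patients, samples or tests are added. The stated power will probably be less favourable.

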### **2.7.2 Immunogenicity**

All immunogenicity analyses in this study are exploratory. All patients in the STM study group will have serum samples collected at Day 1/Visit 1 and at Visit 5 (~28 days postvaccination dose 4) to assess a T-cell dependent antibody response by gpELISA. In addition, a subset of study patients (n ~ 1000) in both the STM and HM populations will participate in the ELISPOT substudy and undergo testing for VZV T-cell responses by IFN- $\gamma$  ELISPOT assay. The geometric mean titer (GMT) or geometric mean count (GMC) and geometric mean fold rises (GMFR) for both the gpELISA and ELISPOT will be provided by vaccination group at scheduled time points (see Section 1.7) for the HM and STM populations separately. A longitudinal regression model will be used to estimate the fold difference at these time points between the vaccination groups, while adjusting for the prevaccination titers (see Section 3.5.5.2) for the HM and STM populations separately. Other exploratory analyses will also be performed to determine whether these VZV-specific immune responses are associated with protection against HZ using Cox proportional hazards models in the combined STM and HM populations.

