### **3.5.4.2 Immunogenicity Analysis Populations**

#### **Per Protocol Immunogenicity (PPI) Populations**

The immunogenicity summaries and analyses will be provided for the PPI population. To be included in this population, patients must:

- (1) Have received all 4 vaccination doses
- (2) Have not reported any exposure to varicella/HZ within 4 weeks prior to blood draw
- (3) Have not develop any suspected varicella/HZ before the relevant blood sampling
- (4) Have not received medical treatments (such as blood products, immunoglobulin therapy) that may interfere with one or both of the proposed immunogenicity measurements.

Based on criterion (4), some patients may be excluded from only one of the 2 immunogenicity analysis (gpELISA, ELISPOT). The final determination of patients excluded from one or both immunogenicity analyses, and thereby the composition of the Per Protocol immunogenicity analysis populations, will be made prior to the final unblinding of the database and will be documented in a separate memo.

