### 3.5.5.1.1 Analysis of Vaccine Efficacy on Incidence of HZ Cases

The primary efficacy endpoint is the incidence of HZ in the vaccine and placebo groups in the STM population, defined as the number of HZ cases per 1000 person-years of follow-up from study enrollment to the end of study. Vaccine efficacy for HZ ( $VE_{HZ}$ ) is defined as the relative reduction of the hazard rate of HZ in the V212 group compared with that in the placebo group in STM population. The primary statistical hypothesis for the primary efficacy is  $H_0: VE_{HZ} \leq 25\%$  versus  $H_1: VE_{HZ} > 25\%$ .

To address the primary hypothesis, a Cox proportional hazards regression model in VZV vaccine and placebo recipients stratified by age (< 50 years of age versus  $\geq 50$  years of age based on a MITT population as described in section 3.5.4.1) will be used as the primary analysis to compare the incidence of HZ between the vaccine and placebo groups. The study time period in the primary analysis will be from the enrollment to the stop date of HZ surveillance. Patients who do not develop HZ will be censored at the stop date of HZ surveillance. The follow-up time for patients who develop HZ will be from the enrollment to their HZ onset date. For the interim analysis, this stop date will be the corresponding database cutoff date for the analysis. Efron's method will be used to handle ties in event times.

A key supportive analysis will include calculation of  $VE_{HZ}$  using a PP population as described in section 3.5.4.1 based on Cox proportional hazards regression model. The study time period in the primary analysis will be from the date of Dose 4 to the stop date of HZ surveillance. The model and covariate adjustment will be similar to that noted in the MITT approach. In addition, incidence of HZ and  $VE_{HZ}$  will also be summarized by age group (50 to 59, 60 to 69, and 70+) as exploratory analyses.

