### 3.5.5.2 Analysis of Vaccine Immunogenicity

All immunogenicity analyses are exploratory in this study. The key immunogenicity endpoints include the GMT and the GMFR from prevaccination (Visit 1) at (Day 1 [prior to Dose 1], to Visit 5 [28 to 60 days Postdose 4]) for the VZV antibody titers as measured by gpELISA in all subjects in STM group. A linear mixed longitudinal model will be used on the natural log transformed antibody titers, for the comparison of GMT between 2 vaccination groups across the time points after vaccination. The longitudinal regression analysis model developed by Liang and Zeger [52] will include prevaccination antibody titers and postvaccination antibody titers as response variables. The covariates in the analysis model will include vaccination group, continuous age, visit (indicator for baseline or postvaccination) and vaccination group-by-visit interaction. The antibody titers will be natural-log-transformed in the analyses. The fold-difference between the vaccine and placebo groups and the corresponding 95% CI at the respective visit will be obtained from this model. This analysis will be based on the per-protocol approach. For patients who receive treatments that may interfere with the measurements of VZV-specific antibody response (including those receiving immunoglobulin therapy) or who report an exposure to varicella/HZ within 4 weeks prior to blood draw, or who develop suspected varicella/HZ before the relevant blood sampling, the measurements at corresponding time points and thereafter will be excluded from the gpELISA analysis. The summaries of VZV antibody titers at each time point will also be carried out by vaccine lot at each time point. Patients who receive immunoglobulin therapies will be included in VZV IFN- $\gamma$  ELISPOT analysis as described below.

To evaluate the association between the immune responses and the risk of HZ, a Cox regression model will be used, which will use the immune responses measured by gpELISA at baseline and at 28 days postvaccination dose 4 as covariates. The GMT and GMFR will also be summarized at these time points by vaccination group and HZ outcome (patients who developed confirmed HZ during the study versus those who did not).

In addition, Cox proportional hazards model will be used to estimate the relation between the occurrence of HZ and the gpELISA titers. The gpELISA titers will be used as the covariate to obtain a risk ratio for HZ per unit increase in the titer.

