The percent of patients with  $\geq$  2-fold,  $\geq$  3-fold and  $\geq$  4-fold rises in gpELISA at Visit 5 [28 to 60 days Postdose 4] by vaccination group will also be provided.

The proportion of patients achieving seroresponse  $\geq$  400 gpELISA units/mL at Visit 5 [28 to 60 days Postdose 4] will be summarized by vaccination group and by HZ status. A supportive analysis may be provided, including all valid immunogenicity results, regardless of protocol deviations. Patients who reported an exposure to varicella/HZ (if any) will be listed and the corresponding count and proportion will be summarized by vaccination group in the tables regarding the exclusion of patients from the per protocol immunogenicity analyses and a brief description of these patients will be provided in the clinical summary section of the Clinical Study Report.

In addition, direct T cell response to VZV antigen as measured by VZV IFN- $\gamma$  ELISPOT in the ELISPOT substudy participants will be performed at each time point (Day 1 [prior to Dose 1], and Visit 5 [28 to 60 days Postdose 4]). The blood samples will be collected on a subset of  $\sim$ 1000 patients. Similar to gpELISA, VZV IFN- $\gamma$  ELISPOT related summaries and analyses will be considered as exploratory in this study. The same endpoints as for VZV antibody titers measured by gpELISA will be used for GMC as measured by VZV IFN- $\gamma$  ELISPOT. Using the natural log scale of GMC, the analyses will be performed similarly as for gpELISA for the comparison of GMC between 2 vaccination groups and for the evaluation of the association between the GMC and the risk of HZ.

The key immunogenicity measurements will be summarized at each time point (Day 1 [prior to Dose 1], and Visit 5 [28 to 60 days Postdose 4]) by HZ outcome (patients who developed subsequent confirmed HZ during the study versus those who did not) at each time point. It should be noted that VZV IFN- $\gamma$  ELISPOT will be performed in a subset of the study population.

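### The combined STM+HM ELISPOT model of immune response and HZ risk names no disease-population stratum, so its slope may absorb a small between-disease difference

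*Combined protocol and SAP*

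**What the plan says.** Exploratory objective 11 concerns the association of post-vaccination immunogenicity with HZ risk. Section 2.1.4 says "11) will be evaluated in both combined STM and HM populations and individual subpopulation". Section 2.7.2 repeats the combined analysis: immune responses are to be examined for whether they are "associated with protection against HZ using Cox proportional hazards models in the combined STM and HM populations". Section 3.5.7.3 justifies the substudy of about 1000 patients by roughly 70% power for "the study to detect correlation with efficacy for combined STM and HM population when assuming the true correlation is one unit increase of log scaled" post-dose 4 ELISPOT count reducing HZ risk by 18%, with SDs of 2.2 (HM) and 1.6 (STM).

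The models are in section 3.5.5.2. One is a Cox regression "which will use the immune responses measured by gpELISA at baseline and at 28 days postvaccination dose 4 as covariates". The other uses the titer alone: "The gpELISA titers will be used as the covariate to obtain a risk ratio for HZ per unit increase in the titer". Both are written for gpELISA, which is measured in STM only (section 2.5.3, Table 2-2; section 3.1.2.4). ELISPOT, the assay measured in both populations, is then to be analysed in a similar way, "and for the evaluation of the association between the GMC and the risk of HZ". Neither model names disease population. Where the plan intends a stratum in the primary analysis it says so: section 3.5.5.1.1 describes "a Cox proportional hazards regression model in VZV vaccine and placebo recipients stratified by age". Section 3.5 states that no separate SAP will be issued.

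**The concern.** A model written for one population is carried over to an analysis of two. The protocol supplies both ingredients of confounding by disease. Section 3.1.2.2 (item 4) reports lower ELISPOT counts in HM than in STM. Section 3.1.1.1 gives an HZ incidence of 31 per 1000 person-years in HM and section 3.1.1.2 gives 12 in STM; section 1.3 gives 23 to 56 and about 19. If HM patients tend to have low counts and more HZ for reasons unrelated to the count, a pooled slope will lean towards higher response, lower risk, even when the count predicts nothing within either disease.

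What is at stake is the reading of the correlate-of-protection result, in the analysis for which the substudy was sized.

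**Working it through.** **Inputs from the documents.** Substudy 500 STM + 500 HM (2.5.3). Design hazard ratio 0.82 per log unit, ln 0.82 = -0.198; SDs 2.2 and 1.6 (3.5.7.3). HM response lower, direction only (3.1.2.2). Interim futility looks at 68 HM and 48 STM cases, each 50% of target (3.5.1), which imply targets of about 136 and 96. Their sum, 232, agrees with 174 cases being 75% of the combined target (Appendix 6.3).

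**Assumed.** HM response 1.5-, 2- or 3-fold lower; normal log responses; two-sided alpha 0.05 for the power check.

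**The plan's own figure.** Expected substudy cases under the original targets: 500 x 136/2568 = 26.5 HM and 500 x 96/2696 = 17.8 STM, total 44.3. Power = Phi(0.198 x sqrt(information) - 1.96).
- Population-specific variances: 26.5 x 4.84 + 17.8 x 2.56 = 173.7, power 0.744; with 90% of cases usable, 0.699.
- Average variance 3.70: 44.3 x 3.70, power 0.719.

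The stated figure of about 70% is reproduced.

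**Rate ratio R (HM/STM).** Case targets: (136/2568)/(96/2696) = 0.0530/0.0356 = 1.49. HM cohort rate against the STM planning rate (2.7.4): 31/17 = 1.82. Cohort rates: 31/12 = 2.58.

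**Pooled slope.** Set the STM mean to 0 and the HM mean to -g. Let beta be the within-population log hazard ratio, with w = R/(1+R). With rare events and equal group sizes, the unstratified Cox slope b equates two means of log response:
- among cases: w(-g + 4.84 beta) + (1-w)(2.56 beta)
- among those at risk, weighted by exp(bx): p(-g + 4.84 b) + (1-p)(2.56 b), where p = aH/(aH+aS), aH = exp(-gb + 4.84 b²/2), aS = exp(2.56 b²/2)

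R is the realised ratio of population rates.

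With beta = 0, to first order ln HR = -(w - 0.5) g/V, where V = 3.70 + g²/4. For a 2-fold gap, g = 0.693 and V = 3.82:
- R = 1.5: w = 0.600, ln HR = -0.100 x 0.693/3.82 = -0.018, HR 0.982
- R = 31/12: w = 0.721, ln HR = -0.221 x 0.693/3.82 = -0.040, HR 0.961

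Solving exactly for gaps of 1.5-/2-/3-fold:

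| R | Pooled HR, true HR 1.00 | Pooled HR, true HR 0.82 |
|---|---|---|
| 1.0 | 1.000 / 1.000 / 1.000 | 0.826 / 0.830 / 0.839 |
| 1.3 | 0.993 / 0.988 / 0.982 | 0.814 / 0.816 / 0.820 |
| 1.49 | 0.989 / 0.982 / 0.974 | 0.808 / 0.808 / 0.811 |
| 1.82 | 0.984 / 0.974 / 0.961 | 0.800 / 0.798 / 0.797 |
| 2.58 | 0.976 / 0.961 / 0.942 | 0.787 / 0.781 / 0.777 |

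**Simulation check.** 1500 trials per setting, about 41-42 cases, log gaps 0.3-1.1.
- Unstratified mean HR: 0.945-0.997 when the truth is 1.00, and 0.775-0.814 when it is 0.82, over rate ratios 1.47-2.58.
- Stratified by population: 0.998-1.004 and 0.816-0.821.
- With no true association, the chance of a significant protective slope (nominal 2.5%) was 2.6-6.7% at R = 1.47 and 4.3-12.7% at R = 2.58 unstratified, against about 2-3% stratified.
- Adding the baseline response (assumed correlation 0.6) at R = 1.81 and log gap 0.69 changed the null HR from 0.974 to 0.987, so it reduced the tilt without removing it.
- Shorter HM follow-up in the same setting gave 0.977.

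**The case against.** The strongest reply is that the unstratified model is read from silence. The Cox models in 3.5.5.2 were written for an STM-only assay, where a disease stratum would be meaningless, and carrying them over as similar does not forbid one. The power figure even leans the other way: 3.5.7.3 gives a separate SD for each population and no mean gap, and about 70% comes out of the within-population information that a stratified fit would use. This stands to the extent that a reader who infers that the plan prescribes an unstratified fit goes further than the text. The text leaves the choice open, with no separate SAP to settle it.

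Second, the gap size is unknown. Its direction comes from a Phase I study of the heat-treated vaccine and describes post-dose responses; nothing is given for placebo recipients, half of this substudy. This stands, and it is why the size is conditional.

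Third, the effect is small against the noise. With about 38 usable cases (fewer than 44.3, since 3.5.4.2 drops patients with suspected HZ before sampling) and a variance near 3.9, the SE of the log hazard ratio is 1/sqrt(38 x 3.9) = 0.08. The null shifts at R = 1.49, 0.011 to 0.026, are 0.1 to 0.3 SE. This also stands.

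Fourth, separate-population fits are already planned and the analysis is exploratory. Those fits can expose a disease artefact, but they do not correct the combined slope.

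**Conclusion.** The point holds as a minor gap in specification. Fitted with only the listed covariates, the combined ELISPOT model may fold a between-disease difference into its slope. Given assumed 1.5- to 3-fold gaps, the spurious hazard ratio under no association is about 0.97-0.99 at the case-target rate ratio and 0.94-0.98 at 31 v 12. Under the design slope the estimate moves from 0.82 to about 0.81 and 0.78-0.79 respectively.

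A reader might infer that the pooled slope must exaggerate protection. The documents do not support that: they give no gap size, and under the design slope the tilt vanishes at R = 1.3 with a 3-fold gap and reverses at R = 1.0, because the lower HM response then legitimately explains some or all of the HM excess.

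A reader might also infer that the power of about 70% is wrong now that the HM arm has closed. That is not shown. The figure is a rationale for substudy size and agrees with the original case targets. Current power cannot be derived, since 3.5.7.3 gives no alpha or event count and the final HM case count is not given.

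**What to change.** In 3.5.5.2, add one sentence: the combined ELISPOT Cox model of immune response and HZ risk is stratified by disease population (STM v HM). Present the separate-population fits already planned under objective 11 beside it.

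The cost is that sentence. Disease population is a randomization stratum (3.2.12), so no new data are needed, and section 3.5 allows changes to exploratory analyses to be recorded, with reasons, in the study report. Fixing the model before unblinding also removes a later choice between pooled and stratified results. Labelling the power in 3.5.7.3 as the original-design figure would help readers but is optional.
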